6.2.16.1 Detailed Data Collection and Study Analyses

Each data point and analysis is listed here in order to evaluate unmet acceptance criteria endpoints. Refer to the study-specific Operations Manual (separate from this protocol) for a concise listing of data collection and analyses per the various study scenarios.

Data in bold, black font will only be collected once in this study, and will not be re-collected when the study donor returns for their second donation.

6.2.16.2 Study Donor Selection: Consent and Demographics

Consent will be obtained from all study donors prior to the collection of demographic information and any study-related screening, tests or blood donation.

Data collected and samples processed during study donor selection are as follows:

- **Consent obtained (Yes/No)**
- **Informed Consent date and time**
- Inclusion/Exclusion criteria
- **Date of birth**
- **Gender**
- **Race**
- **Ethnicity**
- **Height**
- Weight
- Concomitant Medications
- Medical History
- Donation History
- Body temperature
- Blood Pressure
- Pulse
- Hct/Hgb (finger stick)
- **Randomization**

Study Protocol

Clinical Investigation to Evaluate the New Health Sciences Hemanext® Oxygen Reduction System for Leukoreduced Red Blood Cells with CP2D Anticoagulant and AS-3 Additive - Pivotal Trial

Protocol #: CLIN-0001

Date: 28 Nov 2017

Page 33 of 65

For the purpose of this study:

- Concomitant medications will include all study donor self-reported medications (e.g., prescription medication and/or over the counter medications and nutritional supplements) that the study donor takes or has taken within the last 14 days.
- Medical history will include all study donor self-reported chronic diseases for which the study donor is currently being treated and any surgeries the study donor experienced within the previous 6 months.
- Donation history will include whether the study donor is a first-time donor and, if not, when the study donor's last donation occurred. This data will be considered in the presence of a vaso-vagal-related adverse event.
- Sites will have the option to perform the hematocrit and/or the hemoglobin analysis via whole blood obtained by finger stick. Only the analysis performed will be recorded.

6.2.16.3 Collection: Pre-Collection, Collection and Unit Transfer

Data regarding whole blood donation and study donor sample collection and sample processing are listed below. The collection set's identifier numbers will be recorded. Routine phlebotomy will be conducted for venous access and blood donation per the IFU. A sample of the study donor's native (non-anti-coagulated) whole blood will be drawn from the diversion bag and aliquots will be placed in tubes for the indicated analyses.

Data in bold, black font will only be collected once in this study, and will not be re-collected when the study donor returns for their second donation.

Items followed by an “*” are analyses performed on the pre-collection study donor sample.

- System manufacturer
- Part number/Product code
- Lot #
- Filter ID
- Collection date
- Donation start time (“Needle in”)
- Donation end time (“Needle out”)

Study Protocol

Clinical Investigation to Evaluate the New Health Sciences Hemanext® Oxygen Reduction System for Leukoreduced Red Blood Cells with CP2D Anticoagulant and AS-3 Additive - Pivotal Trial

Protocol #: CLIN-0001

Date: 28 Nov 2017

Page 34 of 65

- Collection room temperature
- Procedural IFU confirmation (Yes/No)
- Adverse event documentation
- **Sickle Cell Trait ***
- Viral Markers *
- **Blood typing (ABO) with Rh factor ***

For the purpose of this study:

- For the procedural IFU confirmation, a response indicative of a deviation from the IFU will result in a prompt to record a protocol deviation in a separate Comments eCRF or other log.
- The study donor's evaluability confirmation will reflect the criteria listed in section 5.3.5.1 which defines each item that could impact evaluability.
- For the adverse event documentation, a response indicative of the occurrence of an adverse event will result in a prompt to record adverse event details in a separate Adverse Event eCRF.

6.2.16.4 Pre-filtration Storage and Sampling

Following transfer to the medical laboratory, whole blood mixed with anticoagulant will be stored prior to filtration. Samples for analysis will be obtained immediately prior to filtration. Two (2) plasma samples will be processed from the pre-filtration unit just prior to filtration and frozen for future analysis in instances of confounding data in subsequent analyses.

Pre-filtration data/specimen collection and sample processing are as follows:

- Unit placed in pre-filtration storage: time and temperature
- Time pre-filtration samples obtained
- WB NLR Unit Pre-sample Gross Weight
- WB NLR Unit Post-sample Gross Weight
- Spun Hematocrit
- CBC
 - WBC Count
 - RBC Count
 - MCV
 - MCH

Study Protocol

Clinical Investigation to Evaluate the New Health Sciences Hemanext® Oxygen Reduction System for Leukoreduced Red Blood Cells with CP2D Anticoagulant and AS-3 Additive - Pivotal Trial

Protocol #: CLIN-0001

Date: 28 Nov 2017

Page 35 of 65

- MCHC
- RDW
- PLT Count
- Total Hemoglobin
- Hematocrit
- Supernatant Hemoglobin
- Two (2) reference plasma aliquots

6.2.16.5 Filtration (Leukoreduction)

The whole blood unit will be filtered for leukoreduction per the study IFU and under Study Arm-specific conditions.

Filtration data collection is as follows:

- Filtration Start: time and temperature
- Head Height
- Prime Time
- Filtration End: date and time
- Drain Time
- Filter Weight (following filtration completion)
- Procedural IFU confirmation (Yes/No)

For the purpose of this study:

- For the procedural IFU confirmation, a response indicative of a deviation from the IFU will result in a prompt to record a protocol deviation in a separate Comments eCRF or other log.

6.2.16.6 Post-filtration

The unit will be weighed, sampled, and re-weighed.

- Sampling time and temperature
- Filtered WB Unit Pre-sample Gross Weight
- Filtered WB Unit Post-sample Gross Weight
- CBC
 - WBC Count
 - RBC Count

Study Protocol

Clinical Investigation to Evaluate the New Health Sciences Hemanext® Oxygen Reduction System for Leukoreduced Red Blood Cells with CP2D Anticoagulant and AS-3 Additive - Pivotal Trial

Protocol #: **CLIN-0001**

Date: 28 Nov 2017

Page 36 of 65

- MCV
 - MCH
 - MCHC
 - RDW
 - PLT Count
 - Total Hemoglobin
 - Hematocrit
- Supernatant Hgb
- Spun Hematocrit
- rWBC Count

6.2.16.7 Filtered Whole Blood Separation

Following the completion of filtration, the filtered whole blood units are to be processed into additive PRBCs and PPP. The first step of this process involves centrifugation of the filtered whole blood unit using a hard spin method followed by expressing the PPP from the RBCs (no data is collected relative to plasma expressing).

Separation data collection is as follows:

- Centrifugation time and temperature
- Centrifuge Make
- Centrifuge Model
- Centrifuge Serial #
- Centrifuge Rotor #
- Centrifuge Cup Type
- Centrifuge Duration
- Centrifuge RCF
- Centrifuge Brake
- Centrifuge Temperature

For the purpose of this study:

- Standard information regarding each centrifuge used will be captured prior to the initiation of study activities. Only deviations from the standard equipment will be entered into the eCRF.

Study Protocol

Clinical Investigation to Evaluate the New Health Sciences Hemanext® Oxygen Reduction System for Leukoreduced Red Blood Cells with CP2D Anticoagulant and AS-3 Additive - Pivotal Trial

Protocol #: CLIN-0001

Date: 28 Nov 2017

Page 37 of 65

6.2.16.8 Baseline Sampling

The AS-3 is mixed with the RBCs per the IFU. The RBC units will be sampled for Baseline tests. If the LR-RBC is in the CP arm it will then be placed in 1-6°C storage for 42 days post-collection.

Baseline data collection and sample processing are as follows:

- Time AS-3 added to RBC unit
- IFU confirmation
- Sampling time
- Sampling room temperature
- Pre-sample Gross Weight
- Post-sample gross weight
- CBC
 - WBC Count
 - RBC Count
 - MCV
 - MCH
 - MCHC
 - RDW
 - PLT Count
 - Total Hemoglobin
 - Hematocrit
- Spun Hematocrit
- RBC morphology
- Supernatant Hemoglobin
- ATP
- 2,3-DPG
- SO₂
- pCO₂
- HCO₃
- pH
- Potassium

Study Protocol

Clinical Investigation to Evaluate the New Health Sciences Hemanext® Oxygen Reduction System for Leukoreduced Red Blood Cells with CP2D Anticoagulant and AS-3 Additive - Pivotal Trial

Protocol #: CLIN-0001

Date: 28 Nov 2017

Page 38 of 65

- Sodium
- Glucose
- Lactate
- RBC Morphology
- Time RBC placed in refrigerated storage
- Storage temperature

For the purpose of this study:

- For the procedural IFU confirmation, a response indicative of a deviation from the IFU will result in a prompt to record a protocol deviation in a separate Comments eCRF or other log.

6.2.16.9 Hemanext Processing (IP only)

If the unit is in the IP arm it will be transferred to the ORB and will undergo the Hemanext process per the Hemanext IFU.

Hemanext Processing data collection are as follows:

- Lot #
- ORB Gross Weight (net weight should be < 370g)
- Time ORB placed on agitator
- Time ORB removed from agitator
- IFU confirmation

For the purpose of this study:

- For the procedural IFU confirmation, a response indicative of a deviation from the IFU will result in a prompt to record a protocol deviation in a separate Comments eCRF or other log.

6.2.16.10 Post –Hemanext Processing (IP only)

After undergoing the Hemanext process the unit will be transferred to the HSB and placed in 1-6°C storage for 42 days post-collection.

Post-Hemanext processing data collection and sample processing are as follows:

Study Protocol

Clinical Investigation to Evaluate the New Health Sciences Hemanext® Oxygen Reduction System for Leukoreduced Red Blood Cells with CP2D Anticoagulant and AS-3 Additive - Pivotal Trial

Protocol #: CLIN-0001

Date: 28 Nov 2017

Page 39 of 65

- Sampling date and time
- Sampling room temperature
- Pre-sample Gross Weight
- Post-sample gross weight
- CBC
 - WBC Count
 - RBC Count
 - MCV
 - MCH
 - MCHC
 - RDW
 - PLT Count
 - Total Hemoglobin
 - Hematocrit
- Spun Hematocrit
- Supernatant Hemoglobin
- Time RBC placed in refrigerated storage

For the purpose of this study:

- For the procedural IFU confirmation, a response indicative of a deviation from the IFU will result in a prompt to record a protocol deviation in a separate Comments eCRF or other log.

6.2.16.11 LR-RBC Bacterial Culture Samples (ONLY for units intended for in vivo autologous transfusion)

5-7 days prior to infusion, units intended for transfusion as part of the in vivo cohort must be cultured. Units evaluated as “+” will not be transfused. **Items in bold, underlined blue font refer specifically to in vivo cohort-specific data and analyses.**

- **Sample date**
- **Pre-sample unit gross weight**
- **Post-sample unit gross weight**
- **Outcome of bacterial culture (+/-)**

Study Protocol

Clinical Investigation to Evaluate the New Health Sciences Hemanext® Oxygen Reduction System for Leukoreduced Red Blood Cells with CP2D Anticoagulant and AS-3 Additive - Pivotal Trial

Protocol #: CLIN-0001

Date: 28 Nov 2017

Page 40 of 65

- **If “+”, then date study donor notified not to return for in vivo study.**

6.2.16.12 21-day Analyses

On day 21 post baseline, RBC units will be analyzed.

21-day RBC data point collection and analyses are as follows:

- Sampling date and time
- Sampling room temperature
- Pre-sample Gross Weight
- Post-sample gross weight
- CBC
 - WBC Count
 - RBC Count
 - MCV
 - MCH
 - MCHC
 - RDW
 - PLT Count
 - Total Hemoglobin
 - Hematocrit
- Spun Hematocrit
- RBC morphology
- Supernatant Hemoglobin
- ATP
- 2,3-DPG
- SO₂
- pCO₂
- HCO₃
- pH
- Potassium
- Sodium
- Glucose

Study Protocol

Clinical Investigation to Evaluate the New Health Sciences Hemanext® Oxygen Reduction System for Leukoreduced Red Blood Cells with CP2D Anticoagulant and AS-3 Additive - Pivotal Trial

Protocol #: **CLIN-0001**

Date: 28 Nov 2017

Page 41 of 65

- Lactate
- RBC Morphology
- Time sample returned to refrigeration

6.2.16.13 LR-RBC 42-day Analyses

On day 42 post baseline, RBC units will be analyzed.

42-day RBC data point collection and analyses are as follows:

- Unit Sample date and time
- Pre-sample Gross Weight
- Post-sample gross weight
- CBC
 - WBC Count
 - RBC Count
 - MCV
 - MCH
 - MCHC
 - RDW
 - PLT Count
 - Total Hemoglobin
 - Hematocrit
- Supernatant Hemoglobin
- Spun Hematocrit
- SO₂
- pCO₂
- HCO₃
- pH
- Potassium
- Sodium
- Glucose
- Lactate
- ATP

Study Protocol

Clinical Investigation to Evaluate the New Health Sciences Hemanext® Oxygen Reduction System for Leukoreduced Red Blood Cells with CP2D Anticoagulant and AS-3 Additive - Pivotal Trial

Protocol #: CLIN-0001

Date: 28 Nov 2017

Page 42 of 65

- 2,3-DPG
- ATP Rejuvenation
- 2,3-DPG Rejuvenation
- RBC Morphology
- Time sample returned to refrigeration

6.2.16.14 RBC in vivo recovery and survival (ONLY for units selected for the in vivo study)

Items in bold, underlined blue font refer specifically to in vivo cohort-specific data and analyses.

Donors participating in the in vivo cohort will have an additional 2-4 weeks between donations to ensure washout from prior in vivo survival procedures.

- **Double radiolabel % recovery**
 - **24 hours (+/- 1hour)**
- **Double radiolabel % survival- 28days**
 - **24 hours (+/- 1hour)**
 - **48 hours (+/- 4 hours)**
 - **72 hours (+/- 8 hours)**
 - **1 week (+/- 1 day)**
 - **2 week (+/- 1 day)**
 - **3 week (+/- 1 day)**
 - **4 week (+/- 1 day)**
- **RBC Microparticles**
- **RBC Metabolomics panel**
- **Pregnancy test**
- **Bacterial Culture**

6.2.16.15 Blood Product Disposition

Each whole blood unit collected in the study will generate one unit of LR-RBC. All LR-RBC units will be stored by the site after completion of the study until written consent to discard the units is obtained from the Sponsor. Written consent to discard blood products will not be required for units with a confirmed positive infectious disease result. All Plasma units will be discarded.

Study Protocol

Clinical Investigation to Evaluate the New Health Sciences Hemanext® Oxygen Reduction System for Leukoreduced Red Blood Cells with CP2D Anticoagulant and AS-3 Additive - Pivotal Trial

Protocol #: CLIN-0001

Date: 28 Nov 2017

Page 43 of 65

7.0 Study Risks and Safety Reporting**7.1 Analysis of Risks****7.1.1 Test System**

The IP is regulated as an investigational device and as such, risks associated with the use of the IP are those expected with manual whole blood donation. See sections 7.1.3 and 7.2.2.5 for more information regarding risks associated with manual whole blood donation.

7.1.2 Control System

Refer to the Precautions, Note(s), and Warnings in the Leukotrap® IFU. See sections 7.1.3 and 7.2.2.5 for more information regarding risks associated with manual whole blood donation.

7.1.3 Risk Assessment of Whole Blood Donation

The risks in the manual whole blood donation for this study are the same as any manual whole blood donation. The study donor may experience a vasovagal reaction. These occur in two to four percent (2-4%) of blood donations, regardless of the type. Very rarely, these progress to syncope and/or seizure activities (1:1000). In addition, as with any blood collection procedure, there is the risk of hematoma formation. Whole blood collections will be performed by trained staff at each site that will recognize the early signs of an adverse reaction and will discontinue the collection and administer appropriate aid to minimize the severity of a reaction under the direction of the Principal Investigator or designee. See section 7.2.2.5 for a list of expected adverse events.

7.1.4 Anemia

Current blood collection standard practice defines a maximum whole blood donation for a 110 pound donor within an eight week period as a single unit. Typically, the donor's body replenishes the fluid lost from donation within 24 hours, and replaces the lost red blood cells within two weeks.

With the exception of those study donors who participate in the in vivo cohort, donors will adhere to the collection standard practice. For the in vivo cohort participants who will have an additional ≤ 110 mL of whole blood drawn as part of the RBC recovery assessment at 6 weeks following each donation, they are still well below the two unit volume of red blood cells that would be donated via red cell apheresis which may occur every 16 weeks.

Study Protocol

Clinical Investigation to Evaluate the New Health Sciences Hemanext® Oxygen Reduction System for Leukoreduced Red Blood Cells with CP2D Anticoagulant and AS-3 Additive - Pivotal Trial

Protocol #: CLIN-0001

Date: 28 Nov 2017

Page 44 of 65

To maintain study donors' safety relative to the donation of whole blood for the purpose of this study, Hct or Hgb levels and other applicable inclusion/exclusion criteria will be confirmed prior to each donation.

7.1.5 Risk to Those Conducting the Research

Chosen investigative sites all have long experience in blood collection, storage clinical trials and in vitro studies. All participating staff at the study sites has had training and experience in the handling of potentially biohazardous materials and has been offered hepatitis B vaccine. All phlebotomies are performed in a well-equipped area and only staff with phlebotomy training and experience will perform the whole blood collections. Each of the sites has in-place SOPs for drawing whole blood units and producing and testing blood and blood products. Site staff members are required to have documented SOP training relative to study-related activities. Study donors will be screened with the same criteria used for whole blood donation.

Site staff performing the in vivo portion of the study will be exposed to the radiation attendant to performing the in vivo measurement procedures. Site staff involved in performing the radiolabeled red cell recovery procedures has been trained in handling radioactive materials and wear radiation collection badges that are periodically evaluated. Each investigative site has more than 10 years of experience in the performance of 51Cr and 99mTc radiolabeled red cell recovery procedures and has SOPs in place for the performance of all required procedures. These procedures are well recognized as being safe.

7.1.6 Radiation Exposure

Subjects participating in the in vivo portion of the trial will be exposed to the radiation concomitant to the in vivo measurement procedures. Approximately 15-20 μ Ci of radioactivity will be administered to in vivo subjects in the autologous, radiolabeled packed RBC + whole blood mixture one on day 42. Red cells labeled with 51Cr are frequently used in immunohematology to assess the survival of either allogeneic or autologous red cells. 99mTc labeled red cells are used to measure total blood volume. Each investigative site is experienced in the performance of 51Cr and 99mTc radiolabeled red cell recovery and survival procedures. These procedures are well recognized as being safe. Standard procedures at both sites for radiolabeled red cell recovery measurement include a determination of the radiation exposure history of each subject that will participate in radiolabeled red cell recovery procedures to ensure that, with the addition of the expected exposure in the study, the subject total exposure will not exceed legal limits. In addition, site procedures are expected to minimize the subject radiation dose in the study. There are no known adverse events associated with the low radiation dose that will be administered in this study. Female in vivo subjects must have a negative pregnancy test prior to each reinfusion, be postmenopausal (> 1 year), or surgically sterile.

Study Protocol

Clinical Investigation to Evaluate the New Health Sciences Hemanext® Oxygen Reduction System for Leukoreduced Red Blood Cells with CP2D Anticoagulant and AS-3 Additive - Pivotal Trial

Protocol #: CLIN-0001

Date: 28 Nov 2017

Page 45 of 65

7.1.7 Receiving Allogeneic Blood

Subjects participating in the in vivo portion of the study will receive a reinfusion of a small aliquot of their own (autologous) radiolabeled red cells. The possibility exists that in the case of protocol deviation, the study donor could receive allogeneic (from a different donor) red cells. Possible adverse events that could occur from the infusion of allogeneic blood include:

- Infectious disease transmission
- Hemolytic reaction to non-compatible red cells

Each clinical site has more than 15 years' experience in performing autologous, in vivo, radiolabeled red cell recovery and survival procedures and has current standard procedures that include redundant subject identification procedures to ensure that only autologous blood is reinfused.

7.1.8 Study Donor Benefits

Study donors will not receive any direct benefit from study participation.

7.2 Adverse Events**7.2.1 Monitoring**

This multiple site study is intended to enroll healthy individuals to serve as study donors. Study donors' study activity will be limited to the donation of two units of blood and that the active study duration is expected to be less than 24 hours for each unit. As such, a Data Safety Monitoring Board (DSMB) will not be appointed. Each site will serve as its own primary safety monitor responsible for identifying any adverse events, providing any necessary immediate medical care for a study-related adverse event and the accurate and timely reporting of any adverse events.

Study-related adverse events are defined as those study participant-reported adverse events occurring within 24-hours of donation and/or transfusion. Non-study-related adverse events outside of these periods will not be recorded unless they are of a nature to impact study participant evaluability, safety or data validity.

Reports for events determined by the investigator to be possibly or definitely related to study participation and reports of events resulting in death must be promptly verbally reported to the sponsor within 24 hours, formally reported to the sponsor within 72 hours, and forwarded to the relative site's IRB within the timing dictated by the respective IRB (typically within 3 days).

Study Protocol

Clinical Investigation to Evaluate the New Health Sciences Hemanext® Oxygen Reduction System for Leukoreduced Red Blood Cells with CP2D Anticoagulant and AS-3 Additive - Pivotal Trial

Protocol #: CLIN-0001

Date: 28 Nov 2017

Page 46 of 65

7.2.2 Definitions

The following definitions are based on 21 CFR 314.80, ISO 14155-2011 Clinical investigation of medical devices for human subjects, MEDDEV 2.7/3 Guidelines on Clinical Investigations: Serious Adverse Event Reporting under Directives 90/385/EEC and 93/42/EEC and ICH E6 Good Clinical Practice: Consolidated Guidance.

7.2.2.1 Adverse Event (AE)

An AE is defined as any untoward medical occurrence, unintended disease or injury or untoward clinical sign (including abnormal laboratory finding) in a study donor while enrolled in the clinical investigation, whether or not considered investigational product- related.

Study-related adverse events are defined as those study participant-reported adverse events occurring within 24-hours of donation and/or transfusion. Non-study-related adverse events outside of these periods will not be recorded unless they are of a nature to impact study participant evaluability, safety or data validity.

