7.2.2.2 Serious Adverse Event (SAE)

An adverse event is defined as serious, if it:

- led to death;
- led to a serious deterioration in the health of the patient that:
- resulted in a life-threatening illness or injury,
- resulted in a permanent impairment of a body structure or a body function,
- required in-patient hospitalization or prolongation of existing hospitalization,
- resulted in medical or surgical intervention to prevent permanent impairment to a body structure or a body function;
- led to fetal distress, fetal death, congenital abnormality or birth defect.

The term “life-threatening” is an event that places a patient or study donor at immediate risk of death from the event as it occurred; it does not include an event that, had it occurred in more severe form, might have caused death.

Important medical events that may not result in death, be life-threatening, or require hospitalization may be considered a serious adverse event

Study Protocol

Clinical Investigation to Evaluate the New Health Sciences Hemanext® Oxygen Reduction System for Leukoreduced Red Blood Cells with CP2D Anticoagulant and AS-3 Additive - Pivotal Trial

Protocol #: CLIN-0001

Date: 28 Nov 2017

Page 47 of 65

when, based upon appropriate medical judgment, they may jeopardize the patient or subject and may require medical or surgical intervention.

“Non-serious adverse events” are all events that do not meet the criteria for a “serious” adverse event.

All serious and/or unexpected AEs shall be reported to NHSi within 1 business day of learning of their occurrence. They shall be reported by telephone to a study monitor or other designated individual and recorded within the EDC system on the provided AE electronic form. Additional documentation requested by NHSi will be e-mailed or faxed to NHSi within 1 business day following the request.

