7.2.2.3 Unexpected Adverse Event

AE's for which the nature or severity of which is not consistent with the applicable product information (e.g., Investigator's Brochure or IFU) or been previously identified in the risk analysis report. This includes events that may be symptomatically and pathophysiologically related to an event listed in the labeling, but differ from the event because of greater severity or specificity.

The investigator must determine if the AE was related to the investigational product using the following scoring system:

- Unrelated The AE is clearly NOT related to the investigational product. The AE has no temporal relationship to the administration or use of the investigational product, follows no known or suspected pattern of response, and an alternative cause is present.
- Unlikely related The AE is unlikely to be related to the investigational product. The AE has a temporal relationship to the administration or use of the investigational product, but follows no known or suspected pattern of response, and an alternative cause is present.
- Possibly related There is a reasonable possibility that the event may have been caused by or is linked in a significant way to the research; the AE has a temporal relationship to the administration or use of the investigational product, follows a suspected pattern of response, but an alternative cause is present.

Study Protocol

Clinical Investigation to Evaluate the New Health Sciences Hemanext® Oxygen Reduction System for Leukoreduced Red Blood Cells with CP2D Anticoagulant and AS-3 Additive - Pivotal Trial

Protocol #: CLIN-0001

Date: 28 Nov 2017

Page 48 of 65

- Probably related The adverse event is likely related to the investigational product. The AE has a temporal relationship to the administration of the investigational product or research intervention, follows a known or suspected pattern of response, but an alternative cause may be present.
- Definitely related The AE is clearly related to the investigational product or research intervention. The adverse event has a temporal relationship to the administration of the investigational product or research intervention, follows a known pattern of response, and no alternative cause is present.

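### The 24-hour adverse-event window does not fit the 28-day follow-up of in vivo donors, its wording is ambiguous, and the prompt-reporting trigger skips the probably-related level (minor)

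*Combined protocol and SAP*

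**What the plan says.** Section 7.2.2.1 defines an AE as an untoward occurrence "in a study donor while enrolled in the clinical investigation". It then narrows what counts as related to the study: "Study-related adverse events are defined as those study participant-reported adverse events occurring within 24-hours of donation and/or transfusion". The next sentence sets the recording rule: "Non-study-related adverse events outside of these periods will not be recorded unless they are of a nature to impact study participant evaluability". That sentence continues past the quoted words and also excepts events that bear on participant safety or on the validity of the data. Section 7.2.1 repeats the definition and the rule.

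Section 7.2.1 rests this on donor activity being "limited to the donation of two units of blood and that the active study duration is expected to be less than 24 hours" per unit. Its next paragraph requires prompt reporting of deaths and of events "determined by the investigator to be possibly or definitely related to study participation", with no onset limit.

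Section 7.2.2.2 adds a further route without an onset limit: "All serious and/or unexpected AEs shall be reported to NHSi within 1 business day of learning of their occurrence". Section 7.2.2.3 asks for a causality judgement on five levels: "The investigator must determine if the AE was related to the investigational product using the following scoring system".

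For the in vivo cohort, section 6.2.11 places an infusion 42 days after each donation, with sampling out to 28 days. Step q of section 6.2.16 has these donors return on Days 43-70.

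**The concern.** The basis given in 7.2.1 describes a donor who gives two units and leaves. It does not describe the in vivo donors, who are the only people to receive the stored cells and who attend for study blood draws for four weeks after an infusion. If the recording rule is followed as written, the descriptive AE summary promised in section 5.4 could be thin for this cohort after the first post-infusion day, for expected and non-serious events.

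Two drafting problems compound this. Relatedness is set by elapsed time in one place and by investigator judgement in another. The trigger for prompt reporting also names the levels on either side of probably related, but not that level. What is at stake is the completeness and consistency of the safety record.

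**Working it through.** The plan gives no figure for AE coverage, so there is none to reproduce. The check is calendar arithmetic plus a comparison of the provisions.

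**Inputs.** Window: 24 hours (7.2.1, 7.2.2.1). Time points after infusion: 24 h, 48 h, 72 h, and 7, 14, 21 and 28 days (6.2.11, 6.2.16.14). Infusion: Day 42 after each donation (6.2.11). In vivo donors: 24-28 (Table 2).

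**1. Calendar.** Day 42 + (1, 2, 3, 7, 14, 21, 28) = Days 43, 44, 45, 49, 56, 63, 70, which agrees with the Days 43-70 of step q. Nominal time points beyond 24 h: 7 - 1 = 6 of 7. The 24 h point, with its ± 1 h tolerance, sits at the edge of the window. Post-infusion days outside it: 28 - 1 = 27, and 27/28 = 96.4%.

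**2. Visits, at one per time point.**
- Two infusion courses: 2 × 7 = 14 per donor; 24 × 14 = 336 to 28 × 14 = 392 in all.
- Of these, beyond the window: 24 × 2 × 6 = 288 to 28 × 2 × 6 = 336.
- One course only: 24 × 7 = 168 to 28 × 7 = 196.

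Section 6.2.11 supports two courses. Step s of section 6.2.16, which governs the second unit, repeats steps b to m or b to p and does not list infusion step q. These are visits, not missed events; the documents give no basis for an event count.

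**3. Routes that stay open after 24 hours.**
- Serious or unexpected events (7.2.2.2).
- Deaths, and events judged possibly or definitely related (7.2.1).
- Events meeting one of the exceptions to the recording rule.

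What remains is expected, non-serious events. The unexpected route is narrow: section 7.2.2.5 lists 19 general lines plus 1 for the in vivo cohort, 20 in all, without onset times. They include hematoma, arm pain and tiredness.

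**4. One event, two classifications.** Take an event at 72 hours that the investigator judges possibly related. By the time-only definition it is not study-related; by the next paragraph of 7.2.1 it is promptly reportable. Likewise, a hematoma from a required draw on Day 56 is 14 days after the infusion. It also precedes the next donation, which for this cohort comes at 56 + 14 = 70 to 56 + 28 = 84 days. The clock calls it unrelated although a study procedure caused it.

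**5. Scale against trigger.** The levels are unrelated, unlikely, possibly, probably and definitely. The trigger names the third and fifth. The fourth is defined in 7.2.2.3 as follows: "The adverse event is likely related to the investigational product". The referents differ too: the trigger concerns participation in the study, while the scale concerns mainly the product.

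**6. Data collection.** AE items appear at collection (Table 5 and 6.2.16.3). None appears in 6.2.16.14 or in Tables 6 and 7.

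**The case against.** The strongest reply concerns the wording of the recording rule. It excludes events that are non-study-related and outside the periods. If lateness alone made an event unrelated, the second condition would be redundant. A reading that gives both conditions work drops only events that are unrelated and also late; the 72-hour event is then kept, and 7.2.1 is consistent. This reading is available, but so is the other, because the preceding sentence defines relatedness by time alone. The text is ambiguous, and that is all that is claimed.

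The gap is also small. Infection from a contaminated unit bears on safety and is recordable even though expected. Iron depletion that prevented the second donation would bear on evaluability. Section 7.2.1 makes each site responsible for identifying any AE. Table 4 binds donors to report until 24 hours after their *active study involvement* ends; if that phrase covers the survival visits, donor reporting already spans them, but it is undefined. All of this stands. It leaves mainly mild, expected events, including those from required draws.

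On the trigger, a probably related event is in ordinary language at least possibly related, and the trigger does not cite the scale. The omission is probably a slip, but it does not match the five-level scale that sites must use.

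A reader might infer that all AEs after 24 hours are lost, or that serious ones could be. The routes in step 3 rule that out. Nor can the 96.4% be read as a share of events missed: it weights all days equally. Finally, the separate Operations Manual cited in 6.2.16.1 may already ask about AEs at these visits.

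**Conclusion.** The point holds as a minor one. The 24-hour window and the rationale for it do not fit the in vivo cohort: 6 of 7 nominal time points lie beyond it, and the protocol lists no AE item at those visits. The exposed events are expected, non-serious and later than 24 hours, including those caused by required draws. The wording supports two readings, one of which puts adjacent paragraphs of 7.2.1 in conflict. The trigger omits one level of the scale and uses a different referent.

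Confidence in the wording is high. Whether AEs actually go uncollected cannot be settled without the Operations Manual. The totals of 336-392 visits assume two infusion courses per donor. A reader might infer that section 5.4 is contradicted; it is not, since it promises AE reporting for all enrolled donors without stating a window. No endpoint, sample size or acceptance criterion is affected.

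**What to change.** 1. Extend the 7.2.1 trigger to possibly, probably or definitely related, and align its referent with the 7.2.2.3 scale.
2. For in vivo donors only, add an AE question at each existing Day 43-70 visit and an AE item to 6.2.16.14 and Table 5, with recording through the last scheduled visit of each period. If the Operations Manual already asks, only the protocol text needs changing.
3. Judge relatedness by the 7.2.2.3 scale, and let elapsed time govern only the routine recording window.
4. Correct the activity and duration statement in 7.2.1 for the in vivo cohort, and define *active study involvement*. Reconcile 7.2.1, 7.2.2.1, 7.2.2.2 and Table 4 to one stated window per cohort, leaving the window for in vitro-only donors as it is.

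Cost: a protocol addendum signed by the sponsor and the principal investigators, with local IRB approval (section 9.3); one question at up to 14 existing visits per in vivo donor; and slightly more AE data entry. No visits are added.
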